2.1 Sample size estimation

The glmpower process of SAS9.3 software is applied to estimate the sample size. According to the literature and the preliminary experiment, the mean values of the

VAS score of EA+Carbamazepine group, EA+Placebo group, sham EA+Carbamazepine group, sham EA+Placebo group were 5.23,4.45,5.50,0.00. The standard deviation was 1.6. Under the condition of $\alpha=0.05$, the test efficiency $1-\beta=0.8$, the four groups were allocated with the 1:1:1:1 proportion, the sample size of each group was calculated at least 24. Considering the existence of shedding and other factors, in the premise of guaranteeing the minimum sample size, the sample size was enlarged by 20% to 30 cases in one group, in total 120 cases for 4 groups. Because of the complexity of the sample calculation process of factorial design, the formula is not listed here.

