2.6 Therapeutic effects indexes

Subjects are required to write a verifiable diary card to record their pain symptoms in 24 hours every day. The diary includes the following items: (1) daily attack frequency (spontaneous and provoking pain frequency); (2) provoking factors; (3) average pain intensity(VAS) in the past 24 hours; (4) side effect in the past 24 hours (including side effect of drugs or acupuncture); (5) Is there another analgesia therapies have been adopt ? Please record it.

(1) Indexes of main outcome evaluation

- 1) Change from Baseline Intensity of Pain at 6 months (evaluation of the pain by VAS with 0-10 points).
- 2) Change from Baseline Brief introduction of 2-week pain.

Evaluation method: According to pain diary, we will take average data of 2 weeks before treatment (-2~0 week) as baseline, 2 weeks of treatment phase (1~2 week) as data of treatment phase I, 4 weeks of treatment phase (3~4 week) as data of treatment phase II. During the follow-up period, the pain diary card will be continued in the 2 weeks before 3 months (11~12 week)/6 months (23~24 week) after treatments.

(2) Indexes of secondary outcome evaluation

- 1) Brief Pain Inventory-Facial scale (BPI-Facial)
- 2) Patient Global Impression of Change (PGIC)
- 3) Short-Form McGill Pain Questionnaire
- 4) Short- Form 36 Questionnaire

(3) Research cycle and evaluation time points

The treatment periods of this research are 4 weeks, and the follow-up period is 6 months. The above indexes are observed at the time points of baseline (the same day with the grouping and treatment for the subject), treatment period I (the end of the 2nd week), treatment period II (the end of the 4th week), follow-up period I (3rd months after treatment) and follow-up period II (6th months after treatment). The main outcome indexes will be measured weekly (1th week to 4th weeks) during the treatment period.

(4) Safety evaluation and acupuncture expectation evaluation

The relevant safety indicators during the treatment period and during the follow-up period are recorded at any time on the subjects' adverse event records, which is recorded by the acupuncture physician.

- 1) Safety evaluation of electric needle:

The abnormal acupuncture should be record, including broken needle, left needle, fainting, unbearable acupuncture pain (VAS \geq 8 points), local hematoma, infection and abscess. And the symptoms, average degree and average duration of other discomfort

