2.2 Statistical analysis content

The main analysis contents include:

(1) Four groups of cases distribution: Four groups of the total loss rate and the loss due to adverse events off rate comparison.

(2) Comparability analysis: Compare demographic data and other baseline values to measure the comparability of the four groups.

(3) Compliance analysis: The four groups of patients were compared according to the amount of time to receive the appropriate treatment, the program did not use prohibited drugs.

(4) Effectiveness analysis: Main therapeutic indexes are analyzed by PP and ITT simultaneously. Since this study is a multi-center clinical trial, the effect of the central effect and baseline on the therapeutic effect should be taken into account in the analysis.

(5) Effect factor analysis: such as age, gender, duration, combined medication and other factors on the efficacy.

(6) Safety analysis: First, according to the requirements of adverse reaction correlation list describes four groups of adverse events and adverse reactions (including the number of cases of adverse events and laboratory examination indexes before and after the test "normal turn abnormal cases and different rate), statistical

analysis of the adverse reactions by chi-square test.

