2.3 Statistical analysis method

(1) The measurement data: First of all, the normality test was used. For normal distribution, the t-test, paired t-test, variance analysis and covariance analysis were used to check the data. For non-normal distributions, using rank sum test and paired rank sum test.

(2) The enumeration data: Using the chi-square test, Fisher exact test and so on. The hierarchical data are analyzed by Redit, CMH or other non-parametric tests.

(3) Multi-centers analysis of comprehensive efficacy: The CMH method was used for counting data; Analysis of covariance is used for metering data.

(4) All the statistical tests were double-sided, and the p-value is less than or equal to 0.05 and the difference is statistically significant.

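### The significance rule in SAP 2.3(4) covers every test, and nothing adjusts, orders or labels as exploratory the four secondary scales measured at four visits

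*Combined protocol and SAP*

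**What the plan says.** SAP 2.3(4) gives the only decision rule: "All the statistical tests were double-sided, and the p-value is less than or equal to 0.05 and the difference is statistically significant". It exempts no class of outcome.

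Protocol 2.6(2) lists four secondary scales without ranking them: BPI-Facial, PGIC, Short-Form McGill and SF-36. On timing, Protocol 2.6(3) says "The above indexes are observed at the time points of baseline" and then names four later points: the end of weeks 2 and 4, and months 3 and 6 after treatment. No visit is singled out for the secondary scales.

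SAP 2.2(5) adds an analysis of effect factors, "such as age, gender, duration, combined medication and other factors on the efficacy". That list is open-ended.

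The plan does distinguish main from secondary outcomes:
- Protocol 2.6 puts them under separate headings.
- SAP 2.1 uses LOCF for the main indicators and available cases for the secondary ones.
- SAP 2.2(4) asks for both PP and ITT analyses of the main indexes only.

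None of these provisions says which secondary results may be declared significant.

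**The concern.** Objectives 2 and 3 in Part 1 concern immediate, long-term and post-treatment effects, and whether EA adds to or could replace carbamazepine. The secondary scales are measured across the same period. A team following SAP 2.3(4) to the letter could report one scale at one visit as a statistically significant benefit. The plan contains nothing to tell a reader how many other chances there were for such a result.

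What is at stake is the standing of isolated secondary findings. The main outcomes and the choice of main contrast are outside this point.

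**Working it through.** **Inputs from the documents**
- Threshold: two-sided 0.05 for each test (SAP 2.3(4)).
- Secondary scales: 4 (Protocol 2.6(2)).
- Post-baseline visits: 4 (Protocol 2.6(3)).
- Group size: 30, since 24/(1 - 0.20) = 30 (Protocol 2.1). This is used only in the patient-level simulation below.

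**Assumptions, not in the documents**
- Each scale is tested once at each visit, and SF-36 counts as one score.
- The correlation between test statistics runs from 0 to 0.9.
- The number of treatment contrasts is one or three (two main effects and the interaction of the 2x2 design). The three are taken as independent.

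The plan states no family-wise error rate, so there is no figure of its own to reproduce. A single test gives 5% by definition.

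**Step 1. Size of the family.** 4 scales x 4 visits = 16 tests per contrast.

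**Step 2. One contrast, neither treatment effective.** For independent tests the rate is 1 - 0.95^k. With a common correlation r, it is 1 minus the average over a standard normal Z of [Φ((c - √r·Z)/√(1-r)) - Φ((-c - √r·Z)/√(1-r))]^k, where c is the two-sided 5% critical value.

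| Correlation | One visit, k = 4 | All visits, k = 16 |
|---|---|---|
| 0 | 18.5% | 56.0% |
| 0.5 | 15.6% | 37.4% |
| 0.7 | 13.0% | 26.4% |
| 0.9 | 9.4% | 14.6% |

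For k = 16 the rate is 14.6/5 = 2.9 to 56.0/5 = 11.2 times the nominal 5%.

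**Step 3. Three contrasts.** Two correlation structures were used:
- (a) the common correlation of step 2, giving 1 - (1 - p)^3 with p from that table;
- (b) a product structure, with correlation r between scales and r between visits, so r² for different scales at different visits. The rate for one contrast was simulated and then combined in the same way.

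| r | (a) three contrasts | (b) one contrast | (b) three contrasts |
|---|---|---|---|
| 0.5 | 1 - 0.626^3 = 75% | 43% | 81% |
| 0.7 | 1 - 0.736^3 = 60% | 31% | 67% |
| 0.9 | 1 - 0.854^3 = 38% | 17% | 42% |

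**Step 4. Another route.** SAP 2.3(1) lists analysis of variance, so a single four-group test per scale and visit is also a fair reading. A simulation with 30 patients per group and structure (b) gives about 45% at correlation 0.5, 32-33% at 0.7 and 18% at 0.9.

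Every route gives well over 5%. Counting SF-36 subscales or within-group paired tests would add to the number of tests.

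**The case against.** **The rule is generic.** SAP 2.3(4) may be no more than a statement of sidedness and threshold. No section orders a separate test for each scale at each visit, so the 16-test family is a construction. This stands as a caution on the exact rates. Still, the sentence covers all tests and the plan supplies no narrower one.

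**Secondary outcomes are already subordinate.** This stands in part. A reader might infer that the plan has no hierarchy at all, or gives secondary results equal standing with the main outcome. The separate headings, missing-data rules and analysis sets contradict that. What is missing is any limit within the secondary set.

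**A false secondary claim is not shown to be likely.** A reader might infer odds above one half. For one contrast at correlation 0.5 or more, the rate is below 50%. The 81% figure needs three contrasts assumed independent and the looser correlation structure. It cannot be quoted alone or set beside the 37% as if on the same basis.

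**Effect factors are not necessarily subgroups.** A reader might infer that SAP 2.2(5) plans subgroup tests, and that its four named factors carry a false-positive rate of 1 - 0.95^4 = 18.5%. The text speaks of factors acting on efficacy and mentions neither subgroups nor interactions. If they are prognostic factors, a significant age effect is not a false treatment claim, so no error rate is attached to them here.

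**Conclusion.** The point holds as a cheap improvement. The plan's only significance rule applies to every test, and nothing restricts its use within the secondary set. Under that rule, the chance of at least one false significant secondary result for one contrast is about 3 to 11 times 5%: 37% at correlation 0.5, between 15% at 0.9 and 56% at 0. With three independent contrasts and correlations of 0.5 to 0.9, it runs from about 81% down to 38%.

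The inflation is firm, but its size is not, because the documents give neither the correlations nor the number of contrasts. The text does not support the stronger statements that a false claim is likely whatever the analysis, that main and secondary outcomes rank equally, or that subgroup claims are planned.

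**What to change.** Add to SAP 2.3(4):

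> For efficacy, the p <= 0.05 decision rule applies to the main outcome analysis. Secondary outcomes and effect-factor analyses are exploratory, reported as estimates with 95% confidence intervals; p-values are nominal and no claim of significance is made from them.

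The opening words matter. Confining the threshold to the main outcome without them would also remove it from the safety, loss, baseline and compliance comparisons in SAP 2.2, which should stay as they are.

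In SAP 2.2(5), replace the open list with a closed one and label it exploratory. Where a factor is meant to modify the treatment effect, use baseline factors only and test the treatment-by-factor interaction. Combined medication needs care here, because it may include emergency medication taken after randomisation (Protocol 2.5).

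A confirmatory testing order for the secondary scales is not proposed. It would need a main-outcome gate, and Protocol 2.6(1) lists two main outcomes without saying which one opens it.

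The cost is wording only, with no extra patients, visits or data. The downside is that isolated secondary or effect-factor results can no longer be presented as statistically significant findings.

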2.4 Statistical software

SAS 9.3 software analysis.
